7.2.5 Protection of thyroid function

Blockade of ^{131}I -uptake in the thyroid gland is to be ensured by administration of stable iodine e.g. potassium iodide. For guidance on potassium iodide dosing, the investigators should refer to the FDA's guidance "Potassium iodide as a thyroid blocking agent in radiation emergencies" or the European Association of Nuclear Medicine (EANM) guidance on thyroid protection with potassium iodide during ^{131}I -meta-iodobenzylguanidine (^{131}I -mIBG) therapy (Giammarile et al. 2008, Eur J Nucl Med Mol Imaging). Alternative, more intensive thyroid protective schemes with potassium iodide that are according to institutional or local standard of care may be prescribed at the discretion of the investigator but must be documented. Potassium iodide may be given with juice or soft drink (e.g. cola) to mask taste.

In addition to potassium iodide, Cytomel (liothyronine sodium or equivalent) should be given at 25 $\mu\text{g}/\text{day}$ if weight is less than 25kg or at 50 $\mu\text{g}/\text{day}$ if weight $\geq 25 \text{ kg}$.

Treatment with potassium iodide and Cytomel should be initiated 1 week prior to each ^{131}I -omburtamab infusion in a cycle and continue until 2 weeks after ^{131}I -omburtamab infusion in the same cycle. Thyroid protection is administered in each treatment cycle. Sites will document the treatment regimen for thyroid protection prescribed and patients or caregivers will provide a written diary documenting that the potassium iodide and Cytomel has been taken as instructed by the site.

7.2.6 Participant compliance

Clinical personnel at the site will record in the source notes the timing and site of all administrations of IMP. Any reasons for non-compliance should be documented.

7.3 Concomitant therapy

7.3.1 Therapy allowed during the trial

Any treatment needed for patient wellbeing (including supportive care) that will not interfere with IMP administration may be given at the discretion of the investigator. Detailed information about treatments administered following ^{131}I -omburtamab administration will be captured in the electronic case report form (eCRF). Additional anti-cancer and supportive care treatments are allowed after MRI has been assessed after the last dose at week 9.

- **Prohibited therapy and procedures during weeks -3 to 9**

- Additional anti-cancer therapy during the treatment cycle(s) of ^{131}I -omburtamab
- Additional IMP
- Additional hematological support is not allowed if administered within 1 week prior to IMP administrations

7.4 Treatment after discontinuation of IMP

Any treatment deemed safe and justified by the investigator can be administered according to clinical practice and at the discretion of the investigator.

8 ENDPOINTS

8.1 Efficacy

8.1.1 Primary endpoint

1. OS rate at 3 years after the first treatment dose of ^{131}I -omburtamab.

8.1.2 Secondary endpoints

1. CNS/LM PFS at 6 and 12 months will be estimated based on the time from first treatment dose to CNS/LM progression or death from any cause. Patients alive without CNS/LM progression at time of analysis, will be censored at last date of disease evaluation without evidence of progression.
2. OS at 12 months will be estimated based on the time from first treatment dose to death by any cause. Patients alive at time of analysis, will be censored at last date known to be alive.
3. ORR assessed as a combination of partial response and complete response as defined by the Response assessment in Neuro-Oncology (RANO) group criteria for brain metastasis (Lin et al, 2015) or leptomeningeal metastases as defined by EANO-ESMO criteria (Le Rhun et al, 2017). ORR will be assessed at 6 months after the first treatment dose of ^{131}I -omburtamab
4. ORR according to CSF cytology. Response is defined as a complete response when CSF converts from positive at baseline to negative after treatment with ^{131}I -omburtamab
5. Whole-body, organ, blood, and CSF radiation dosimetry.
6. Pharmacokinetic analysis of activity in blood and CSF including derivation of best-fit uptake and/or clearance parameters (half-times, maximum value) of time-activity concentration curves and of I-131 residence times (i.e., cumulated activity) concentrations (in $\mu\text{Ci}\cdot\text{h/g}$).
7. The frequency, type, and duration of treatment-emergent severe adverse events and serious adverse events, including clinically significant laboratory abnormalities. All adverse events will be graded according to Common Terminology Criteria for Adverse Events (CTCAE), version 4.0.
8. Performance assessment to monitor gross changes in neurological function is performed at week 26 and subsequently every 6 months during trial period.
9. The rate of ADA occurrence assessed three weeks after the first and second treatment dose of ^{131}I -omburtamab

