¹⁰ If CSF sample is positive for abnormal cells or outside reference ranges for any of the following: 1. total protein 2. glucose 3. cell count, it must be repeated within 4 weeks of the sample at screening. If abnormal CSF glucose (CTCAE \geq Grade 2) is obtained, a fasting serum glucose is to be obtained at next patient visit. At week 26, the CSF analysis should include cytology only.

¹¹ Treatment with potassium iodide and Cytomel should be initiated 1 week prior to each ¹³¹I- omburtamab infusion in a cycle and continue until 2 weeks after ¹³¹I- omburtamab infusion in the same cycle..

¹² Thyroid protection should be initiated 1 week prior to IMP administration. See section 7.2.5 for further details.

¹³ Thyroid protection should be initiated 1 week prior to next IMP administration – this is only applicable for week 4 and not week 8. See section 7.2.5 for further details.

¹⁴ Beginning 24 hours before ¹³¹I-omburtamab administration please see section 6.1.2.

¹⁵ Given 1-2 hours prior to ¹³¹I-omburtamab administration, including oral acetaminophen/paracetamol and antihistamine (e.g., diphenhydramine), please see section 6.1.2¹⁶
Drawn and held for culture if elevated body temperature after dosing suggests infection rather than expected response to intracerebroventricular dosing.

¹⁷ Dose reduction: 50% (25 mCi) for patients < 1 of age and 33% (33.5 mCi) for patients age 1 year to < 3 years of age, respectively.

¹⁸ Non-SAE's captured from signing the informed consent form (ICF) to dosing should be recorded as medical history. AEs should be reported until 3 weeks after the last IMP administration. SAE's should be captured from signing the ICF. Starting at week 4 (for patients receiving only one cycle) and starting at week 8 (for patients receiving both cycles) only SAEs considered related to ¹³¹I-omburtamab or new onset of cancers regardless of causality should be reported.

¹⁹ Limit to therapy related to cancer.

²⁰ In case fertile women (experienced menarche prior to screening or during treatment, until week 8) are enrolled; pregnancy testing should take place at screening, at week 4 and week 8, and at follow-up at week 26.

²¹ Follow-up at week 26 (24-29 weeks after first treatment) and Long-term follow-up visits at Weeks 52, 78, 104, 130 & 156 (\pm 4 weeks) can be done at referral site.

²² If done at referral site imaging parameters as required in the Imaging Manual should be followed to the extent possible.

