9.1.2 Secondary endpoints

9.1.2.1 ***CNS/LM Progression-Free Survival (CNS/LM PFS) at 6 and 12 months***

The time frame for CNS/LM PFS will be from first treatment dose of ^{131}I -omburtamab to time of documented CNS/LM progression or death from any cause. CNS/LM PFS will be censored at last date of disease evaluation without evidence of CNS/LM progression. CNS/LM PFS at 6 and 12 months will be estimated using Kaplan-Meier methods.

9.1.2.2 ***OS at 12 months***

OS at 12 months will be estimated by Kaplan-Meier methods following the same time and censoring scheme as the primary endpoint.

9.1.2.3 ***Objective response rate (ORR)***

Response will be assessed at 6 months (week 26 visit) after the first treatment dose of ^{131}I -omburtamab as a combination of best overall partial or complete response at 5, 10, and 26 weeks. Assessments will follow the Response assessment in Neuro-Oncology (RANO) group criteria for parenchymal metastasis (Lin et al, 2015) or as defined by EANO-ESMO for leptomeningeal metastases (Le Rhun et al, 2017). The evaluation comprises MRI scans, CSF cytology, and clinical assessments. ORR at week 26 is defined as the proportion of patients with response at week 26 from the total population of patients with radiographically evaluable disease at baseline.

9.1.2.4 ***Dosimetry and PK analysis for ^{131}I -omburtamab***

An interim analysis, evaluating the dosimetry and pharmacokinetic endpoints as well as available safety and efficacy data, will be conducted on data from patients having received at least one treatment cycle1 (both dosimetry and treatment dose) prior to January 1st, 2020. Starting January 1st, 2020, no further patients will be administered dosimetry doses.

9.1.2.5 ***Performance assessment***

Since most if not all patients will have received prior crano-spinal and/or whole brain irradiation, late side effects for such previous therapies are difficult to distinguish from ^{131}I -Omburtamab inflicted toxicities in CNS. However, to evaluate gross changes in neurological

function, performance test will be conducted during screening and at weeks 26, 52, 78, 104, 130 and 156. The scales to be used are: Lansky < 16 years and Karnofsky \geq 16 years.

9.1.2.6 ***Anti-Drug-Antibodies characterization***

A quantitative assay to assess anti-drug antibodies (ADAs) will be developed. The assay will be developed and validated using “cold” labeled omburtamab (^{125}I -omburtamab).

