9.2.2 CSF for cytology, total protein, glucose and cell count

CSF for cytology, total protein, glucose and cell count should be assessed during screening and at week 4, 8, and 26. If positive, it must be repeated within 4 weeks of the positive sampling.

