12 STATISTICAL METHODS AND DETERMINATION OF SAMPLE SIZE

12.1 General Overview

The data will be summarized in tables, as appropriate, showing the number of patients with non-missing data (n), mean, standard deviation, median, minimum, and maximum for continuous data and showing counts and percentage for categorical data. Data will also be listed as deemed appropriate. All statistical analyses will be performed and data appendices will be created by using SAS version 9.0 or later.

All statistical tests will be two-sided with an α level of 0.05.

The Statistical Analysis Plan (SAP) will describe in detail the analyses presented below. Furthermore, handling and presentation of data including baseline data and other trial assessments will be described in the SAP. The selection of an appropriate control group from available external data is briefly described below but will be described in full detail in the SAP. Patient characteristics that may be considered in the selection of the control group include, but are not limited, age at diagnosis, MYCN amplification status, International Neuroblastoma Staging System stage at diagnosis, International Neuroblastoma Pathology Classification (favorable vs. unfavorable), time to first relapse, site of relapse, and lactate dehydrogenase level.

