12.3 Efficacy Analysis

The FAS will be used for all efficacy endpoints. Additionally, the primary and secondary endpoint analyses will also be performed on the PPS. The primary endpoint of the OS rate at 3 years as well as OS at 12 months, and CNS/LM PFS at 6 and 12 months with corresponding 95% confidence intervals, will be estimated using Kaplan-Meier methods using the FAS. The comparison to external controls (OS only) will be exploratory and performed using multiple cox regression taking into account the most important prognostic factors identifiable in the historic data. The median OS and CNS/LM time and associated 95% confidence interval will be calculated. Results will be displayed with Kaplan Meier plots. ORR according to RANO criteria and CSF cytology as well as CSF cytology alone, will be assessed, 95% confidence intervals will be calculated using the Clopper-Pearson exact methodology.

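### A CSF-cytology complete response can rest on one unconfirmed negative sample, and the baseline sample and the role of repeats are undefined

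*Combined protocol and SAP*

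**What the plan says.** Cytology response is a separate secondary endpoint. Section 8.1.2, item 4 reads: "Response is defined as a complete response when CSF converts from positive at baseline to negative after treatment". Item 3, the imaging-based objective response rate (ORR), fixes a time of 6 months; item 4 fixes none.

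Section 9.2.2 sets the sampling: CSF "should be assessed during screening and at week 4, 8, and 26". It then adds: "If positive, it must be repeated within 4 weeks of the positive sampling". It has no matching rule for a negative sample.

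Table 1 footnote 10 gives a different repeat rule. After a positive or otherwise abnormal sample, "it must be repeated within 4 weeks of the sample at screening". Protein, glucose or cell count outside the reference range also triggers it. Footnote 5 places the screening CSF within 3 weeks before the first infusion, so a repeat within 4 weeks of it may fall before or after dosing.

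For the combined ORR, which includes CSF cytology, Section 9.1.2.3 scores response "as a combination of best overall partial or complete response at 5, 10, and 26 weeks". It states no such rule for cytology alone, and those weeks do not match the CSF schedule.

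Section 12.3 covers the analysis of cytology alone only by saying that "95% confidence intervals will be calculated using the Clopper-Pearson exact methodology". Section 12.1 leaves detail to the SAP, and the combined document has no further text on this endpoint.

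**The concern.** A patient who is negative at week 4 and positive at week 8 meets item 4 as it is worded. If cytology sometimes misses malignant cells that are present, each further sample gives a patient with persistent disease another chance of one negative result, and nothing in the definition takes that result back. In a single-arm trial no comparison group shows how often this happens. An exact confidence interval describes sampling error and cannot correct misclassification.

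Two related gaps add to this. No text says which pre-dose sample is the baseline when a screening sample has been repeated. No text says whether a repeat result enters the endpoint. If a negative repeat of a post-dose positive counted, positives would be retested and negatives would not, which favours response.

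What is at stake is how a named response rate can be interpreted. Between 32 and 50 patients are to be enrolled (Section 6.8) and the number positive at baseline is not given, so a few misclassified patients could move the rate visibly. Leaving the counting rule open also allows it to be chosen after the data are seen.

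**Working it through.** **1. Nothing to reproduce.** The documents state no expected rate, threshold or power for cytology response.

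**2. Inputs.** From Section 9.2.2: three scheduled post-dose samples, at weeks 4, 8 and 26. Assumed, because the documents are silent: a false-negative probability *f* per sample of 10% to 40%, and independence between samples from one patient.

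**3. Chance that a persistently positive patient is called a responder.**

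- Any negative in three: 1 − (1 − f)³.
- Two consecutive negatives in three (patterns NNN, NNP, PNN): f³ + 2f²(1 − f) = f²(2 − f).
- Only two samples, weeks 4 and 26: any negative 1 − (1 − f)²; both negative f².

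| Rule | f = 10% | f = 20% | f = 30% | f = 40% |
|---|---|---|---|---|
| Any negative in three | 27.1% | 48.8% | 65.7% | 78.4% |
| Two consecutive in three | 1.9% | 7.2% | 15.3% | 25.6% |
| Any negative in two | 19% | 36% | 51% | 64% |
| Both of two negative | 1% | 4% | 9% | 16% |

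**4. Effect on the reported rate.** Reported rate = π × P(called responder if cleared) + (1 − π) × P(called responder if persistent). Assume a true conversion rate π of 40% and no false positives.

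- f = 10%: any of three 0.40 + 0.60 × 0.271 = 56%; two consecutive 0.40 + 0.60 × 0.019 = 41%.
- f = 30%: any of three 0.40 + 0.60 × 0.657 = 79%; two consecutive 0.40 + 0.60 × 0.153 = 49%.
- f = 0: both rules give 40%.
- f = 0 with specificity 0.95: one fixed visit gives 0.40 × 0.95 = 38%; two consecutive gives 0.40 × 0.95² × 1.05 = 38%; any of three stays at 40%. The confirmed rule can therefore err slightly low when false positives occur.

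**5. Repeats, at f = 20%, if a negative repeat counted.**

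- Footnote 10 governs, so no post-dose repeats: 48.8%.
- Section 9.2.2 governs, with the week-8 sample serving as the repeat of a week-4 positive (five samples): 1 − 0.8⁵ = 67%.
- Section 9.2.2 governs, with a separate repeat after each positive (six samples): 1 − 0.8⁶ = 74%, an upper bound.

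**6. Correlation.** If all samples from a patient gave the same result, both rules would reduce to f, for example 20% each at f = 20%, and confirmation would gain nothing. The gap in the first two table rows is therefore the most favourable case for confirmation.

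**The case against.** The strongest reply is that item 4 is silent rather than permissive. It does not say that any single negative suffices, the best-across-visits wording belongs to the combined ORR, and detail is left to the SAP. That is fair as far as it goes: a reader might infer a stated any-negative rule, and there is none. But a definition that one negative satisfies, with no visit and no requirement that it hold, leaves that count open.

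A reader might also infer that negatives are never retested. The documents do not support this: CSF is scheduled at weeks 4, 8 and 26 whatever the earlier result. The gap is that the definition does not use the later results.

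A third inference is that the plan retests post-dose positives to the advantage of the drug. That depends on Section 9.2.2 prevailing over footnote 10, and on repeats counting, which no text says. Nor does any text say that a patient already negative on a pre-dose repeat would be scored as converted; such a repeat could equally expose a false-positive baseline. What stands is that the baseline sample is undefined.

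The size is rightly challenged as well, since both the false-negative rate and independence are assumed.

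Finally, confirmation has a price. A week-8 negative can be confirmed only at week 26, after Section 7.3.1 allows other anti-cancer therapy, so response becomes partly durability under later treatment. This stands, and the fix has to deal with it.

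**Conclusion.** The point holds as a defect of definition. One unconfirmed negative can satisfy the endpoint even when a later scheduled sample is positive. Upward bias follows if cytology sensitivity is below 1 and false positives are rare. It would grow if negative repeats of post-dose positives counted.

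The documents do not support a claim that the rate is biased upward by any known amount. The range of 27% to 78% against 2% to 26% illustrates false-negative rates of 10% to 40% with three independent samples. With perfect sensitivity the any-negative rule adds nothing, and with strongly correlated samples confirmation removes little.

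The endpoint is one of nine secondary endpoints and is reported as a proportion with an interval. No test, threshold or decision is attached to it, and the primary OS analysis is untouched. The change is worth making because it is cheap; the trial does not depend on it.

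**What to change.** Amend item 4 of Section 8.1.2 and carry the rule into the SAP:

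- **Baseline and denominator.** Baseline is the last CSF cytology before the first dose. The denominator is the patients positive at that sample.
- **Response.** Negative at two consecutive available scheduled samples (weeks 4, 8, 26; weeks 4 and 26 if there is no week-8 sample), with no positive between them.
- **Repeats.** A repeat triggered by a positive cannot create a response. A scheduled sample keeps its scheduled status even if it also serves as a repeat.
- **Supportive reporting.** Give the any-negative rate alongside. List first negatives at week 26 separately as unconfirmed, and flag confirmations obtained after other anti-cancer therapy.
- **Consistency.** Reconcile Section 9.2.2 with Table 1 footnote 10, and align the weeks named in Section 9.1.2.3 with the sampling schedule.

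The cost is wording only, because the samples are already scheduled. The downside is a lower stated rate. A first negative at week 26 cannot be confirmed, because no later CSF is scheduled, and a patient with a single post-dose sample cannot be a responder. Patients treated for one cycle can still qualify on weeks 4 and 26.

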8.2 Safety

8.2.1 Safety endpoints

Safety data will be collected via AE and SAE reporting during the trial and graded according to CTCAE, version 4.0. Abnormal findings at physical examination and vital signs will also be monitored and any clinically significant abnormalities should be reported as AEs. Adverse events including Clinical Laboratory Adverse Event (CLAE; as defined in section 10.1.1).

9 PROCEDURES AND ASSESSMENTS

9.1 Efficacy assessments

9.1.1 Primary endpoint

OS rate at 3 years. The time frame for assessment of OS will be from the first treatment dose of ^{131}I -omburtamab to time of death from any cause. OS will be censored at last date of contact. Survival at 3 years will be estimated by Kaplan-Meier methods.

9.1.2 Secondary endpoints

9.1.2.1 ***CNS/LM Progression-Free Survival (CNS/LM PFS) at 6 and 12 months***

The time frame for CNS/LM PFS will be from first treatment dose of ^{131}I -omburtamab to time of documented CNS/LM progression or death from any cause. CNS/LM PFS will be censored at last date of disease evaluation without evidence of CNS/LM progression. CNS/LM PFS at 6 and 12 months will be estimated using Kaplan-Meier methods.

9.1.2.2 ***OS at 12 months***

OS at 12 months will be estimated by Kaplan-Meier methods following the same time and censoring scheme as the primary endpoint.

9.1.2.3 ***Objective response rate (ORR)***

Response will be assessed at 6 months (week 26 visit) after the first treatment dose of ^{131}I -omburtamab as a combination of best overall partial or complete response at 5, 10, and 26 weeks. Assessments will follow the Response assessment in Neuro-Oncology (RANO) group criteria for parenchymal metastasis (Lin et al, 2015) or as defined by EANO-ESMO for leptomeningeal metastases (Le Rhun et al, 2017). The evaluation comprises MRI scans, CSF cytology, and clinical assessments. ORR at week 26 is defined as the proportion of patients with response at week 26 from the total population of patients with radiographically evaluable disease at baseline.

9.1.2.4 ***Dosimetry and PK analysis for ^{131}I -omburtamab***

An interim analysis, evaluating the dosimetry and pharmacokinetic endpoints as well as available safety and efficacy data, will be conducted on data from patients having received at least one treatment cycle1 (both dosimetry and treatment dose) prior to January 1st, 2020. Starting January 1st, 2020, no further patients will be administered dosimetry doses.

9.1.2.5 ***Performance assessment***

Since most if not all patients will have received prior crano-spinal and/or whole brain irradiation, late side effects for such previous therapies are difficult to distinguish from ^{131}I -Omburtamab inflicted toxicities in CNS. However, to evaluate gross changes in neurological

function, performance test will be conducted during screening and at weeks 26, 52, 78, 104, 130 and 156. The scales to be used are: Lansky < 16 years and Karnofsky \geq 16 years.

9.1.2.6 ***Anti-Drug-Antibodies characterization***

A quantitative assay to assess anti-drug antibodies (ADAs) will be developed. The assay will be developed and validated using “cold” labeled omburtamab (^{125}I -omburtamab).

9.1.2.7 ***Anti-Drug-Antibody effects on PK and Safety.***

The ADA characterization will deliver occurrence rate of neutralizing antibodies in blood and cerebrospinal fluid (CSF) of exposed patients. Potential associated effects of any neutralizing ADA's on ^{131}I -omburtamab pharmacokinetics (PK) in blood and CSF and safety will be investigated.

9.1.2.7.1 *ADA effects on PK*

Radioactivity counts in blood and CSF will be measured at the following time points after treatment with ^{131}I -omburtamab:

- 1h after treatment
- 6h after treatment
- 24 after treatment
- 7 days after treatment.

The analysis will comprise an intra-patient comparison of PK parameters from the two dose administrations in patients with and without presence of neutralizing ADAs in blood or CSF.

9.1.2.7.2 *ADA effects on Safety*

The analysis will comprise a comparison of reported safety events after the second dose administration in patients with and without presence of neutralizing ADAs in blood or CSF.

9.2 **Other assessments**

9.2.1 **Hematology and clinical chemistry**

Hematology and clinical chemistry will be measured by a local laboratory during screening and in all following treatment cycles and will assess liver and kidney function (ALT, AST, alkaline phosphatase, albumin, bilirubin, BUN, glucose and creatinine), total protein and serum electrolytes (sodium, potassium, chloride and bicarbonate). Complete differential blood count, including eosinophils and platelets, will be performed during screening and in the cycles up to the follow-up at week 26. Thyroid stimulating hormone (TSH)/ free and total T4 to be assessed at screening, pre-dose week 1 and 4, pre-dose week 5 and 8, week 26 if applicable and weeks 52, 78, 104 130 and 156..

If abnormal serum glucose (CTCAE \geq Grade 2) is obtained, a fasting serum glucose is to be obtained at next patient visit. AE reporting of hyperglycemia will require fasting values to assess CTCAE grading.

